8. RISKS TO SUBJECTS

Hyperoxia has been explored in various disease states. While meta-analysis in myocardial infarction did not show an increase in mortality, hyperoxia has been shown to have negative cardiovascular and hemodynamic effects in cardiac patients. In some, but not all cardiac disease states, there were decreases in heart rate and cardiac output and increases in systemic vascular resistance⁴⁰. These potential decreases in cardiac output and increases in

systemic vascular resistance could negatively impact stroke patients, especially those with perfusion dependent lesions.

The most commonly proposed potential harm from hyperoxia therapy is the increased production of reactive oxygen and nitrogen species that not only may contribute to reperfusion injury, but may also lead to hyperoxic lung injury. Rodent MCAO models suggest that this risk is low given there was no evidence of such effects when therapy was instituted immediately after the ischemic event¹⁴⁻¹⁹. This issue has also been evaluated in rodent models and in human models in critically ill patients. In an endotoxemia model (induced by the administration of lipopolysaccharide derived from E.coli), brief hyperoxia with a PaO₂ of ~400mmHg for 3.5 hours in humans resulted in no change in the ability to mount a cytokine and inflammatory response⁴⁴. Both hyperoxic and control subjects had similar patterns of expression of tumor necrosis factor alpha (TNF- α), interleukin-6 (IL-6), IL-8, or IL-10 in response to endotoxemia. Additionally, hyperoxia treatment did not clinically alter the leukocyte population produced in response to endotoxemia, nor the ability for neutrophils to undergo phagocytosis. Hyperoxic lung injury has been demonstrated in patients exposed to hyperoxia for long periods of time but has not been evaluated in those with brief hyperoxia exposures^{45,46}. Thus, by limiting the oxygen therapy in this clinical trial to no more than 4 hours, the study will minimize this potential risk.

Further safety concerns regarding possible increased mortality resulting from hyperoxia therapy were also raised with a multicenter retrospective study that determined the 28-day mortality in all mechanically ventilated intensive care unit (ICU) stroke patients (including ischemic stroke, subarachnoid hemorrhage (SAH), and intracerebral hemorrhage (ICH)). This study found an increased mortality in all stroke patients found to be hyperoxic (defined as a 24-hour post-admission PaO₂ >300mmHg)⁴⁷. However, upon subgroup analysis, increased mortality was only seen in the hyperoxic SAH and ICH groups compared to normoxic controls, and there was no significant difference in mortality in the AIS patients exposed to hyperoxia (43% in-hospital death at 28 day in normoxic patients vs 57% in hyperoxic patients, p=0.13)⁴⁷. This was further supported by a second study of ICU stroke patients being mechanically ventilated that failed to demonstrate an association between oxygenation level (PaO₂) and mortality⁴⁸. The safety of hyperoxia in AIS patient was also questioned in a recent unpublished clinical trial (NCT00414726) studying hyperoxia, that randomized patients to room air or 45L/min via facemask. The trial was terminated early, after enrolling only 85 participants, for safety concerns⁴⁹. However, upon closer blinded review of the results, only one death in each group was determined to be possibly related to the therapy. The remainder (16/43 deaths in the hyperoxia group, 6/41 deaths in normoxia group) were determined to be unrelated to therapy. However, the exact cause of death was not reported. Additionally, there similar rates of cardiac disorders between the hyperoxia vs normoxia groups (4/43 vs 5/41) and pulmonary related adverse events (3/43 vs 2/41). As such, a similarly designed clinical study in Europe began recently. Taken together, the data suggests that the safety of hyperoxia therapy is disease-specific and short exposures to hyperoxia in AIS patients is safe. However, the exact immediate and long-term effects of brief hyperoxia in AIS are not fully understood.

In this study, the patients will have both a venipuncture for serum samples and an arterial blood gas (ABG) analysis performed. While venipuncture for various laboratory analyses is part of the standard of care for stroke patients, only a select number of patients would normally be exposed to this procedure – usually limited to patients with questionable respiratory status. ABGs carry the risk of pain associated with the needle puncture and increased risk of bleeding and/or hematoma formation, arterial vasospasm causing distal

ischemia that affects the distal circulation in patients without good collateral blood flow, and infection. These are significant risks compared to venipuncture. However, these complications from an ABG are still rare when performed by trained personnel. Additionally, while there are no alternatives to verify arterial oxygen content, the number of ABGs performed is limited to a single draw after the institution of hyperoxia treatment to verify hyperoxia.

10. POTENTIAL BENEFITS TO SUBJECTS

Preclinical and limited human data suggests that this treatment may improve neurologic outcomes in a disease that is a leading cause of world-wide morbidity and mortality. The study intervention has the potential to increase cerebral blood flow to the penumbral tissue at risk for cell death, decrease the production of free radicals leading to reperfusion injury, help maintain the blood-brain barrier, and thereby decrease the final infarction volume and improve neurologic outcomes in stroke patients^{14-17,20-22,26,28,58}. Additionally, in a study that provided supplemental oxygen via a 40% venturi mask compared to nasal cannula in severe stroke patients, there was also a non-significant trend toward lower rates of in-hospital mortality and co-morbidities such as fever, pneumonia, and respiratory failure⁵⁸.

By participating in this study, patients will be part of research that furthers the understanding of the potential therapeutic role of hyperoxia. Additionally, to date, there are limited potential therapeutic interventions for stroke, with few patients being eligible for tPA or presenting with a lesion and timeframe that is amenable to endovascular therapy. This study will shed light on these potentials for this novel therapy for stroke.

11. COSTS FOR PARTICIPATION

There will be no additional costs to the subject resulting from study activities.

12. PAYMENT FOR PARTICIPATION

While participation in the study is voluntary, subjects will be asked to agree to a follow-up telephone interview 3-months after their enrollment. To compensate them for their time, subjects completing all study interventions including this 3-month interview will receive a \$25 gift card or check. This will be disbursed after the completion of the interview by mail. If a subject is unable to complete the study, they will not be paid for their participation. There will be no other forms of compensation and/or reimbursement.

13. SUBJECT WITHDRAWALS

Due to the brief nature of the intervention limited to only 4 hours of therapy, it is not anticipated that many (if any) subjects will be withdrawn by the investigator from the research without their consent. An investigator may discontinue the study intervention for the following reasons: significant study intervention non-compliance (more than 20 minutes of non-compliance with study intervention); if any clinical adverse event (AE), laboratory abnormality, or other medical condition or situation occurs such that continued participation in the study would not be in the best interest of the participant; If the participant meets an exclusion criterion (either newly developed or not previously recognized) that precludes further study participation.

Discontinuation of hyperoxia treatment arm does not mean discontinuation from the study, and remaining study procedures should be completed as indicated by the study protocol. If a clinically significant finding is identified (including, but not limited to: an alternative diagnosis besides stroke, evidence of hypoxia prior to enrollment, baseline requirement of supplemental oxygen use) after enrollment, the investigator or qualified designee will determine if any change in participant management is needed. Any new clinically relevant finding will be reported as an adverse event (AE).

The data to be collected at the time of study intervention discontinuation will include the following: reason for discontinuation; time of discontinuation; medically necessitated interventions as a result of discontinuation.

Participants are free to withdraw from participation in the study at any time upon request. The reason for participant discontinuation or withdrawal from the study will be recorded on the Case Report Form (CRF). Subjects who sign the informed consent form, are randomized and receive the study intervention, and subsequently withdraw, are withdrawn or discontinue from the study, will be not be replaced.

14. PRIVACY AND CONFIDENTIALITY OF SUBJECTS AND RESEARCH DATA

Participant confidentiality and privacy will be ensured through careful data handling procedures. All paper forms for study documentation will be stored in locked cabinets, and only research staff will have access to the documents. Serum samples will be immediately coded into a secure, HIPAA-compliant database (either REDCap or a password-protect secure server at the University of Colorado). All study data will be de-identified after chart extraction and stored in the database to maximize the security of the electronic data. All data will be secured in locked offices and all electronic data will be stored on encrypted servers, as per institutional policy. All computer systems at the University of Colorado Anschutz Medical Campus have the level and scope of security exceeding that established by the HIPAA Security Rules. Imaging data is processed using RAPID AI. In cases where images are not automatically processed by RAPID, i.e. subsequent MRI, these raw DICOM files containing PHI will be processed with RAPID technology within the hospital firewall (see figure above regarding RAPID DUA and de-identification overview). No data will be shared with anyone who is not directly involved with the study, and findings will only be reported in aggregate.

In order to obtain required clinical information, study personnel will require access to the subject's medical charts through eRecord. Only the predetermined information will be reviewed and collected. Subjects will not be re-contacted outside of the scheduled study activities if they have chosen to opt-out of future contact. Data and unused samples will be stored for a minimum of 6 years after the completion of the study.

15. DATA / SAMPLE STORAGE FOR FUTURE USE

The field of biomarkers in stroke research is used to help predict outcomes and better understand the pathophysiology behind stroke is rapidly changing. To ensure simplicity of study design and to enhance the feasibility of this study, only three biomarkers, MMP-9, IL-6 and IL-8 have been chosen upon initial review to be included in biomarker analysis. However, additional biomarkers may also be chosen for further analysis and serum will be stored within the ED Cold Storage space for future analysis that could improve the understanding of the biological mechanism underpinning the effects of hyperoxia in AIS.

These samples will not be analyzed on an individual basis, but rather analyzed and reported in aggregates. Thus, it represents minimal additional risk to study subjects to store the serum for future biomarker analysis. The physical samples will be de-identified and coded such that they may be linked to the clinical information for the patient, which will also be de-identified after all data collection for the study has been completed. All samples will be stored in a HIPAA-compliant, restricted access ED Cold Storage space. Only study personnel will have access to the samples. Samples will be aliquoted into smaller vials to help limit degradation of samples through repeated freeze-thaw cycles for up to 6 years. A password protected document on a UC secure server will be used to track the usage of individual aliquots of samples.

During the conduct of this study, an individual participant can choose to withdraw consent to have biological specimens stored for future research. However, withdrawal of consent with regard to biosample storage may not be possible after the conclusion of this study once samples have been de-identified. Samples will only be released for future analysis after a formal request process. The process will include a request for a COMIRB approved-protocol and/or protocol amendment from an individual or team of individuals associated with this original study. The released sample and accompanying clinical information will be de-identified.

16. DATA AND SAFETY MONITORING PLAN

Only trained research assistants at UCH-Memorial will be responsible for consent of subjects, with support of the site-PI, site-sub-I and/or PI as needed (see consent section for details). The research assistants at UCH-Memorial will be responsible for completion of patient assessments and reporting of potential safety issues and/or protocol violations to the site-PI, site-sub-I and PI. In addition, the PI will review data assessments uploaded to REDCap monthly for completion. Site screening/enrollment logs will be reviewed monthly. Study personnel at both sites will undergo an initial training by the PI at onset of study which will include review of the study protocol, inclusion/exclusion criteria, the consent process, methods of sample collection and processing, patient assessments, and standardized chart review methods. The trained research assistants at both sites will have complete required human subjects research trainings and specific training to ensure accuracy of the NIHSS scoring prior to completing these assessments on any subjects. A standard operating procedures (SOP) manual will also be provided for references. Training will be refreshed annually or sooner if there are protocol changes and/or any compliance concerns.

Safety oversight will be under the direction of a Safety Monitoring Committee (SMC), composed of individuals with the appropriate expertise, including stroke, neurocritical care, and emergency medicine. Members of the SMC will include members of the investigative team. However, measures will be in place to minimize perceived conflict of interest. The SMC will meet at least semiannually to assess safety and efficacy data on each arm of the study.

Assessment of safety measures and adverse events:

Study personnel and the subject's treating physician will regularly monitor subjects for safety measures and adverse events. This includes practices that are associated with routine patient care (i.e. vital sign assessments, assessment of neurologic deterioration, development of respiratory compromise). Specific monitoring includes the following:

1. Vital signs - The determination of need for additional supplemental oxygen in a patient that becomes hypoxic (pulse oximetry < 94%) will be determined by the subject's treating physician irrespective of study interventions. Should a patient be found to require additional supplemental oxygen while enrolled in the study, this will be noted and the patient will continue through the final study assessments. The patient's treating physician will also be responsible for routine monitoring and interpretation of other vital signs such as blood pressure and heart rate. If at study assessment time points the study personnel note a subject to have significant vital sign abnormalities (SpO₂<94%, SBP>200mmHg, DBP>110mmHg, SBP<90mmHg, HR>120, HR<50), the study PI and patient's treating physician will be notified to ensure proper documentation. Interventions will be left to the discretion of the patient's treating physician.
2. Arterial puncture and ABG – Hyperoxia (PaO₂>200mmHg) will be confirmed by obtaining an ABG in subjects. Personnel trained in obtaining arterial punctures (i.e. nurse, physician or respiratory therapist) will be notified and available to obtain the ABG four hours after initiation of study intervention. Standard procedures for obtaining an arterial blood sample will be employed to reduce the risk of complications. To decrease variability between ABG analysis, ABGs will be performed using standard operating procedures. The site of the arterial puncture and correlating extremity will be evaluated for potential complications (increased pain, discoloration, erythema, hematoma formation, bleeding) immediately after obtaining the ABG and at T2.
3. Hemorrhagic conversion – as part of the standard neurological care, patients are monitored for neurological deterioration. Patients exhibiting neurological decline will receive a CT-head and/or further imaging for evaluation of potential hemorrhagic conversion at the discretion of the treating physician. Based on previous studies in AIS, it is expected that between 13-43% of subjects will undergo spontaneous hemorrhagic conversion on imaging⁵⁹. Any such cases will be reported as an adverse event.
4. Development of respiratory compromise – While patients are continuously assessed by their treating medical team, study personnel will specifically assess study subjects at the T0+4hour and T0+24hour evaluations for worsening respiratory status and the need for additional supplemental oxygen. At the final 3-month assessment, patients' medical records will also be reviewed for evidence of respiratory deterioration while the patient was hospitalized and up to this final assessment including: need for additional supplemental oxygen, need for non-invasive positive pressure ventilation, mechanical ventilation, development of pulmonary edema, development of pneumonia.
5. Development of post-stroke infections – Neuroinflammation after a stroke also results in immunosuppression. As such, this places patients at increased risk of post-stroke infections, the two most common being pneumonia and urinary tract infections which may account for up to 30% of deaths after an AIS⁶⁰. Additionally, there may be sex-based differences in post-stroke infections that could be related to underlying hormone status⁶¹. As such, patients will be screened at the 3-month assessment to determine if they experienced any post-stroke hospitalizations and/or treatment for pneumonia, urinary tract infections, sepsis, or other infections. In addition to asking subjects directly at this assessment, their medical record will also be reviewed for re-admissions while it is being reviewed for the above respiratory compromise.

Definition and Classification of Adverse Events: An adverse event means any untoward medical occurrence, unintended sign, symptom, or disease temporarily associated with the use of an intervention in humans, whether or not considered intervention-related. All AEs will be documented and analyzed further. Subjects will be monitored for signs of an AE at T0+4hr and T0+24hours.

An adverse event (AE) or suspected adverse reaction is considered "serious" if it results in any of the following outcomes: death, a life-threatening adverse event, prolongation of existing hospitalization, a persistent or significant incapacity or substantial disruption of the ability to conduct normal life functions. Important medical events that may not result in death, be life-threatening, or require hospitalization may be considered serious when, based upon appropriate medical judgment, they may jeopardize the participant and may require medical or surgical intervention to prevent one of the outcomes listed in this definition.

For adverse events (AEs), the following guidelines will be used to describe severity.

- **Mild** – Events require minimal or no treatment and do not interfere with the participant's daily activities.
- **Moderate** – Events result in a low level of inconvenience or concern with the therapeutic measures. Moderate events may cause some interference with functioning and/or the need for further supplemental oxygen or antibiotic treatment.
- **Severe** – Events interrupt a participant's usual daily activity and may require systemic drug therapy or other treatment. Severe events may include need for mechanical ventilation, vasoactive infusion, are usually considered potentially life-threatening or incapacitating.

The PI will be responsible for determining whether an adverse event (AE) is expected or unexpected. An AE will be considered unexpected if the nature, severity, or frequency of the event is not consistent with the risk information previously described for the study intervention.

The following AEs are considered to be expected:

1. Bleeding and/or hematoma formation at sight of arterial puncture
2. Pain at the sight of arterial puncture lasting after collection of ABG
3. Hemorrhagic conversion in up to ~40% of study subjects

The occurrence of an adverse event (AE) or serious adverse event (SAE) may come to the attention of study personnel during study observation time points or upon review by a study monitor.

All AEs including local and systemic reactions not meeting the criteria for SAEs will be captured on the appropriate case report form (CRF). Information to be collected includes event description, time of onset, clinician's assessment of severity, relationship to study intervention (assessed only by those with the training and authority to make a diagnosis), and time of resolution/stabilization of the event. All AEs occurring while on study must be documented appropriately regardless of relationship. All AEs will be followed to adequate resolution.

Any medical condition that is present at the time that the participant is screened will be considered as medical history and not reported as an AE. However, if the study participant's condition deteriorates at any time during the study, it will be recorded as an AE.

Changes in the severity of an AE will be documented to allow an assessment of the duration of the event at each level of severity to be performed. AEs characterized as intermittent require documentation of onset and duration of each episode.

The study PI will record all reportable events into a database with start dates occurring any time after randomization until completion of the study. At T0+24hours, study personnel will inquire about the occurrence of AE/SAEs since the last observation point. Solicited and unsolicited events will be captured. Unsolicited AEs will be identified by asking participants if they "have noticed anything different since beginning the treatment after the onset of your stroke." Solicited AEs will include: 1) any trouble breathing, 2) development of pneumonia, 3) need for additional oxygen therapy, 4) hemorrhagic conversion of the stroke. Events will be followed for outcome information until resolution or study completion.

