4. STUDY DESIGN

This is a multicenter, prospective, randomized, controlled, feasibility study to evaluate the feasibility of early brief hyperoxia therapy for AIS in the ED and to gather preliminary data on the potential therapeutic and adverse effects of such intervention. It is hypothesized that global hyperoxia treatment in the acute ischemic period of a stroke prior to potential recanalization will decrease infarct volumes and improve neurologic outcomes in AIS patients without increasing the production of markers correlating with ischemic-reperfusion injury and the hyperoxic lung injury. To test this hypothesis, subjects will be randomized equally between the placebo (medical air) and hyperoxia (supplemental oxygen) treatment groups.

[figure not shown]
For the purpose of this study, we define normoxia as a pulse oximetry of 94% or greater, although per AHA guidelines, supplemental oxygen is recommended only in patients with a pulse oximetry of less than 94%⁵⁰. Based on rodent models that targeted systemic hyperoxia with a PaO₂ of 200-400mmHg, hyperoxia will be defined as a PaO₂ of >200mmHg. Previous literature demonstrated that 10-15L/min facemask resulted in the PaO₂ of 425 +/- 43mmHg in patients undergoing cardiac catheterization found to have clean coronary arteries and 403 +/- 49mmHg in those with CAD⁵¹. Thus, treatment with 15L/min should be sufficient to achieve this level of hyperoxia in this study population, and will be confirmed through ABG sampling at 4 hours after initiation of treatment intervention.

Patients who are found to require supplemental oxygen according to AHA guidelines will be provided such intervention with careful documentation of the timing, duration, and dose of supplemental oxygen provided.

The design will proceed as follows: (see Figure 2)

- Randomize subjects between placebo and supplemental oxygen via partial non-rebreather facemask at 15 L/min.
- Collect study measurements
- Perform 3-month follow up for mRS
- The study duration is estimated at 30 months to allow sufficient time for subjects enrollment and completion of their 3 month follow-up

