4.3. STUDY INTERVENTIONS

Enrolled subjects will be randomized to receive either brief hyperoxia treatment (defined as 15L/min supplemental oxygen) or medical air (at 15L/min) via a partial non-rebreather mask for four hours from the time of study initiation (T_1). Supplemental oxygen is routinely used to correct and/or prevent hypoxemia (low blood oxygen content, defined as an arterial oxygen content of less than 60-75mmHg). To avoid invasive monitoring of arterial oxygen content, pulse oximetry is routinely used to monitor for hypoxia with values less than 90-94% considered low in most clinical scenarios. Unfortunately, there are limitations with pulse oximetry and based on the oxyhemoglobin dissociation curve and a SpO_2 of 97% could represent any PaO_2 above ~90mmHg. Thus, pulse oximetry alone is not an ideal mechanism to determine hyperoxia. Based on mouse models, this study targets a PaO_2 of 200-400mmHg in the hyperoxia treatment group. In a previous study of cardiac catheterization patients, delivery of 10-15L/Min facemask oxygen resulted in average PaO_2 in the 400s.

In this study, oxygen is being used as a drug. However, an IND exemption is requested. We feel that the use of oxygen in this scenario to prevent hypoxemia in the ischemic tissue by creating a global hyperoxia environment meets the criteria for an IND exemption. Specifically, this protocol will: be conducted in compliance with requirements for IRB review and the requirements concerning the promotion and sale of drugs; not be in support of a new indication for use or change in labeling or advertising of oxygen; not invoke exemption from informed consent; not involve a route of oxygen administration or dosage level that significantly increase the risks of the drug product. Additionally, there is no consistent predetermined dosage of oxygen that can be universally applied to all clinical contexts to determine who needs supplemental oxygen and at what dose. This decision is left to the clinical judgement of the practicing medical provider. For example, in patients undergoing procedural sedation in the ED, supplemental oxygen may be provided despite having a pulse oximetry reading greater than 92-94% to prevent desaturation. According to the AHA guidelines for stroke patients, hypoxia that they suggest warrants supplemental oxygen use is defined as a pulse oximetry of less than 94%, but the data behind this exact recommendation is also very weak⁵⁰.

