5. *Vital signs* - The determination of need for additional supplemental oxygen in a patient that becomes hypoxic (pulse oximetry<94%) will be determined by the subject's treating physician irrespective of study interventions. Should a patient be found to require additional supplemental oxygen while enrolled in the study, this will be noted and the patient will continue through the final study assessments. The patient's treating physician will also be responsible for routine monitoring and interpretation of other vital signs such as blood pressure and heart rate. If at study assessment time points the study personnel note a subject to have significant vital sign abnormalities (SpO₂<94%, SBP>180mmHg, DBP>110mmHg, SBP<90mmHg, HR>120, HR<50), the study PI and patient's treating physician will be notified to ensure proper documentation. Interventions will be left to the discretion of the patient's treating physician.

Table 1: Schedule of Activities:

Procedures	Baseline/Enrollment ED presentation -T0 (ED arrival +/-60min)	T1 (T0+4hours +/- 20min)	T2 (T0+24hours +/- 4hours)	T3 - Final Assessment (T0+3mo +/- 2weeks)
Informed consent	X			
Demographics	X			
Medical history	X			
Randomization	X			
Administer study intervention		X		
Vital signs: HR, BP, RR, SpO ₂	X	X	X	
ABG		X		
CT-perfusion or CT-head with ASPECTS	X			
Repeat MRI-head (CT-head if unable to get MRI) ^a			X	
Serum sample ^b	X	X	X	
NIHSS	X	X	X	
mRS	X			X
Adverse event review and evaluation		X	X	

^a only routine re-imaging will be obtained
^b tested for selected biomarkers (IL-6, IL-8, and MMP-9)

Assessment of study intervention adherence:

1. Compliance with study interventions will be directly observed at the given time points. If at any observation period a subject is found not to be compliant with the study intervention, medical records will be reviewed to determine the timing of termination of the supplemental oxygen/medical air.
2. All cases of non-compliance with study interventions will be recorded.

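### While study gas is running, SpO2 below 94% and need for added oxygen depend on the assigned gas, so by-arm counts of these two items lean towards hyperoxia

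*Combined protocol and SAP*

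**What the plan says.** Section 4.3 gives both arms 15 L/min by mask, oxygen or medical air, "for four hours from the time of study initiation (T_1"). It expects an inspired oxygen fraction of 0.45-0.9 in the oxygen arm and a PaO2 above 200 mmHg. Section 4 says that this level "will be confirmed through ABG sampling at 4 hours after initiation of treatment intervention".

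Section 16, on respiratory compromise, states that "study personnel will specifically assess study subjects at the T0+4hour and T0+24hour evaluations for worsening respiratory status and the need for additional supplemental oxygen". The schedule in section 7 (Table 1) places these checks at "T1 (T0+4hours +/- 20min") and "T2 (T0+24hours +/- 4hours"). The same paragraph of section 16 adds a three-month chart review that covers the hospital stay. It looks for added oxygen, non-invasive or mechanical ventilation, pulmonary edema and pneumonia.

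One threshold serves both arms. The vital-signs item of section 16 begins "The determination of need for additional supplemental oxygen in a patient that becomes hypoxic (pulse oximetry < 94"%) and leaves the decision to the treating physician. The solicited adverse events include "3) need for additional oxygen therapy", and need for further oxygen also helps to define the moderate severity grade. The safety committee reviews data on each arm at least twice a year.

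Section 4.3 itself notes that "pulse oximetry alone is not an ideal mechanism to determine hyperoxia", because an SpO2 of 97% fits any PaO2 above about 90 mmHg.

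**The concern.** A safety measure should respond to harm in the same way in both arms. Here the assigned treatment acts directly on the measure. A subject on medical air who was enrolled at the permitted SpO2 of 94% crosses the threshold with a one-point fall. A subject on 15 L/min oxygen can lose much more gas exchange before SpO2 reaches 94% or anyone thinks of adding oxygen. The bias favours the arm in which lung harm is suspected.

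It reaches the solicited adverse event, the moderate grade, the chart-review count of added oxygen and the committee's tables by arm. The plan does not ask for on-gas and post-gas events to be shown apart. Since the study is meant to inform a later trial, a table with less hypoxia and less added oxygen on hyperoxia could be read as reassurance about the lungs when it only reflects the gas being breathed.

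**Working it through.** The plan gives no figure for respiratory events, so there is none to reproduce. The check has two parts.

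**1. Are subjects on gas at the checks?**

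Let gas start *s* hours after T0 and run the full four hours, so that it stops at T0 + 4 + *s*. Section 17 aims to start treatment within one hour of ED arrival in 80% of subjects. If T0 is ED arrival, *s* lies mostly between 0 and 1.

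- The T1 window is T0 + 3 h 40 min to T0 + 4 h 20 min. If *s* is above 20 minutes, the whole window falls before gas stops. If *s* is near 0, the check can fall on either side of gas stop.
- The T2 window is T0 + 20 h to T0 + 28 h. With gas stopping at T0 + 4 h to T0 + 5 h, T2 falls between 20 - 5 = 15 h and 28 - 4 = 24 h after gas stop.

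So T1 is usually on gas and T2 is clearly off gas. Two labels blur this. Section 4.3 attaches T_1 to study initiation, whereas Table 1 sets T1 at T0 + 4 h, and Table 1 gives T0 itself a tolerance of 60 minutes around ED arrival.

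**2. How large could the distortion be?**

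The following are assumptions, because the documents give no rates:

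- *p*: true risk during gas of SpO2 below 94% or need for added oxygen, equal in both arms (5% or 10%)
- *m*: share of those events hidden by oxygen (50%, 80% or 100%)
- *q*: off-gas risk, equal in both arms (10%)

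Formulas:

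- On-gas risk: air = *p*; oxygen = *p*(1 - *m*); risk ratio = 1 - *m*
- Pooled risk: 1 - (1 - on-gas risk)(1 - *q*)

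| *p* | *m* | On-gas air vs oxygen | On-gas ratio | Pooled air vs oxygen | Pooled ratio |
|---|---|---|---|---|---|
| 5% | 50% | 5% vs 2.5% | 0.5 | 14.5% vs 12.25% | 0.84 |
| 5% | 80% | 5% vs 1% | 0.2 | 14.5% vs 10.9% | 0.75 |
| 5% | 100% | 5% vs 0% | 0 | 14.5% vs 10% | 0.69 |
| 10% | 50% | 10% vs 5% | 0.5 | 19% vs 14.5% | 0.76 |
| 10% | 80% | 10% vs 2% | 0.2 | 19% vs 11.8% | 0.62 |
| 10% | 100% | 10% vs 0% | 0 | 19% vs 10% | 0.53 |

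For example, with *p* = 10% and *m* = 100%, air is 1 - 0.90 × 0.90 = 19%, oxygen is 1 - 1.00 × 0.90 = 10%, and 10/19 = 0.53.

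Read the other way, an on-gas measure shows no difference when the true risk ratio is 1/(1 - *m*). That is 2 at 50% masking and 5 at 80%.

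For scale only, since the plan contains no such test: take Fisher's exact test at two-sided 0.05, 100 per arm and equal true risk. The chance of a significant result favouring oxygen is about 1.0% at *p* = 5% and 1.4% at *p* = 10% with no masking. On-gas counts alone give 7-38% at *p* = 5% and 19-94% at *p* = 10%, as masking runs from 50% to 100%. Pooling in *q* = 10% brings these to 5-12% and 10-37%.

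**The case against.** Several points on the other side stand, and they limit the claim.

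- **Hypothesis.** A reader might infer that the study's hypothesis of no lung injury is itself compromised. The documents do not support this. Section 4 words the hypothesis in terms of markers, and the plan measures MMP-9, IL-6 and IL-8 in serum. Masking of pulse oximetry does not touch those assays.
- **Invisible deterioration.** A reader might infer that PaO2 could drop from 400 to about 90 mmHg unnoticed. The arterial sample at about four hours would show it. That sample is a single check that hyperoxia was reached and gives no like-for-like comparison of lung function between arms, but the fall would not be hidden.
- **Other measures.** Respiratory safety does not rest on SpO2 alone. The T0 + 24 h check is off gas. Ventilation, pulmonary edema and pneumonia are not defined by SpO2, and trouble breathing is solicited. These do not correct the oxygen-need items, and pooling dilutes the bias without removing it.
- **No planned test.** Section 17 specifies no between-arm respiratory analysis, and the study claims no power for secondary or exploratory outcomes. What is exposed is descriptive tables and committee review, so a false-positive rate such as 94% is not a property of this plan. That figure also needs complete masking and no off-gas events.
- **Data already collected.** Section 16 records onset and resolution times of adverse events, and section 4 requires the timing, duration and dose of supplemental oxygen. The split by gas period can be derived from these; what is missing is the instruction to make it.
- **Post-gas counting is not clean either.** Oxygen begun during gas in the air arm may still be running at 24 hours, which carries the bias forward. Counting only new events removes susceptible subjects mainly from the air arm, which can bias against hyperoxia. The fix has to show both.

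**Conclusion.** The concern holds for the gas period, which usually includes the T0 + 4 h check. In that window SpO2 below 94% and need for added oxygen depend on the assigned gas, the bias runs towards hyperoxia, and the plan does nothing to separate the affected counts. The direction follows from the protocol's own description of the gases, the common threshold and the limits of oximetry.

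The size cannot be derived from the documents. On the assumptions tabulated above, a true ratio of 1 would appear as 0.5 to 0 on gas and as 0.84 to 0.53 once a 10% off-gas risk is pooled in. Lower on-gas risk or weaker masking would bring the pooled ratio closer to 1.

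The documents do not support the stronger reading that respiratory safety as a whole is biased. This is a flaw in the reporting of two items in a feasibility study. It is worth correcting because by-arm safety tables will be read and the correction is cheap.

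**What to change.** 1. Add to the reporting plan that SpO2 below 94% and need for added oxygen, including the solicited adverse event and the part of the moderate grade that rests on oxygen need, are tabulated by arm separately for the on-gas and post-gas periods. Derive the split from the onset times and oxygen timing already recorded. Label the on-gas counts as not comparable between arms.
2. Rest the by-arm respiratory safety comparison on non-invasive or mechanical ventilation, pulmonary edema and pneumonia, together with post-gas oxygen need at T2 and in the chart review.
3. Flag subjects whose added oxygen began during gas, and show the post-gas comparison with and without them.
4. Reconcile T_1 in section 4.3 with T1 in Table 1, so that every check can be classed as on or off gas.

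The cost is a few sentences in the protocol and in the table specifications, with no new visit or test. Fewer events enter the comparison, and some carry-over from the gas period remains. Clinical monitoring and the treating physician's decisions are unchanged.
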